FEAST and ultrabrief RUL ECT patients will be treated identically except as noted below. The traditional d'Elia electrode placement will be used for UB RUL ECT (American Psychiatric Association, 2001), with the frontotemporal electrode tangential to the midpoint of the line connecting the right auditory tragus and the canthus. The posterior electrode will be tangential to the vertex (midpoint of line connecting nasion and inion). Standard stainless steel 2" diameter electrodes will be used. If it is deemed that patients require a change in ECT modality, a switch to either brief pulse RUL or BL ECT will be implememnted, as clinically indicated.

B.8 Assessment of Efficacy

Clinician ratings. Instruments include the HRSD (24-item) (Hamilton, 1967), MADRS (Montgomery and Asberg, 1979), CGI (severity and improvement) (Guy, 1976), and the GAS (Endicott and Spitzer, 1978). A clinical evaluation team independently completes these scales on the basis of conjoint interviews, both at set time points (preECT baseline, 1-2 days after ECT termination) and the HRSD alone is also completed at spaced intervals (weekly during the ECT course). Interviews usually take place between 10 AM-12 PM to minimize variability due to diurnal variation.

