Self-Report ratings. The Inventory of Depressive Symptoms (IDS-SR) (Rush et al., 1985) is completed at baseline, and following completion of the course. This instrument has shown strong psychometric properties and is especially broad in its coverage of depressive symptoms. It has been used in many MDE treatment trials, including STAR*D (Rush et al., 2006).

B.9 Classification of Clinical Outcome and Dropout

Dropout. If, for any reason, there is a lapse of 3 scheduled treatments during a FEAST course (e.g., intercurrent illness, withdrawal of consent), the course is considered terminated. If, for any reason, the patient receives a prohibited psychotropic they are also considered to have dropped out. Patients who withdraw consent for research participation are immediately withdrawn from the research. The Principal Investigator or the Study Physician may withdraw a patient from the protocol at any time if it is deemed in the patient's interest to do so. Examples include emergence of a complicating medical condition, discovery of a previously undiagnosed exclusion criterion, etc.

Response Criteria. Remission is the categorical outcome that has precedence for efficacy determination. However, response status denotes that substantial, but incomplete, benefit has obtained. The a priori criteria for response are consistent across virtually all MDE clinical trials. Based on an assessment 1-2 days following ECT, patients are responders if they have a $\geq 50\%$ reduction in HRSD₂₄ scores relative to preECT baseline. All other patients are nonresponders.

Remission Criteria. Especially when ECT is the treatment modality, the goal is remission and not response (Thase, 2003, Paykel, 2002, McCall, 2014, McCall, 2013). Remitters in this study must satisfy final response criteria and have a 1-wk postECT HRSD ≤ 10 . The remitter criteria are stringent, given the use of the 24-item HRSD and the severity of illness at study entry.

B.10 Assessment of Function and Attitudes Toward Treatment

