Table 5: Schedule of Procedures/Assessments

Assessment or Measurement	Screening Visit (s)	MRI Visit	ECT Weekly Assessments	End Of Acute Study	MRI Visit #2	2 month, 4 month, 6 month follow-up
---------------------------	---------------------	-----------	------------------------	--------------------	--------------	-------------------------------------

Informed Consent	X					
Study Information	X					
Demographics	X					
Medical Workup	X					
SCID and other treatment assessment battery (table 3)	X			X No SCID		
HRSD 24	X		X	X		X
ATHF/medications	X			X		X
Cognitive Battery	X			X		X
MRI scan		X			X	

B.13 Neurophysiology

Four-Channel Ictal EEG. At each treatment, 4 channels of EEG are recorded with the MECTA Spectrum amplifiers (1.4-48 Hz bandpass, -3dB, 12 dB/octave), and digitized and archived with MECTA EMR software. The spatial positioning of the frontal and temporal EEG electrodes, the preparation of each electrode site, and the referencing to ipsilateral linked mastoid EEG electrodes are detailed in a study manual. At each session, impedance of the each referenced pair is determined to be below 5k ohms.

The 4-channel EEG recordings are manually artifactual to remove non-encephalopathic signals. Expert visual inspection is used to define for each session the temporal periods characterized as preictal baseline (20 seconds prior to stimulus delivery), tonic phase (post-stimulus to onset of prominent low wave activity), clonic phase (end of tonic until offset of seizure activity in all channels) and postictal period (20 s following the termination of the seizure). These 4-channel ictal recordings are analyzed in a fashion identical to the procedures we have previously employed, but with the addition of measures of coherence (Luber et al., 2000, Nobler et al., 2000a). Power spectral analyses will be conducted, using a moving Hanning window and apply a Fast Fourier Transform to yield power and coherence data for each electrode site and measurement period for delta, theta, alpha, and beta frequency bands. The 4-channel recordings allow averaging across treatments to enhance reliability of measurement, and examination of cumulative effects (Krystal et al., 1998, Krystal et al., 1996a, Krystal et al., 1997, McCall et al., 1996a).

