The primary analysis for Hypothesis 4 will use all available HRSD₂₄ data (i.e., the intent-to-treat data) from the FEAST and UB RUL ECT samples. A random regression model will be used to examine the relationship between HRSD₂₄ scores and treatment group. Time will be the within-subjects repeated measures factor, site and treatment group the between-subjects factors, with medication-resistance classification and baseline HRSD₂₄ serving as covariates. All interactions with time will be modeled. In secondary analyses, we will also include age, gender, age-at-onset of illness, and duration of current episode as covariates, if pre-screening indicates utility. We will investigate whether HRSD₂₄ scores are linear in time or quadratic, cubic, or piece-wise linear (e.g., hockey-stick shaped). Indeed, in a study comparing several different statistical methods in their sensitivity to ECT treatment groups differences in rate of clinical improvement, we found that the HRSD₂₄ scores over time were frequently nonlinear (Nobler et al., 1997a). The type of analysis conducted on HRSD₂₄ scores will be repeated for secondary analyses with the MADRS, IDS-SR, and CGI-S.

FEAST and UB RUL ECT will also be compared in the categorical outcomes of final remission status (HRSD₂₄ of 10 or less at post-treatment) in a secondary analysis to gauge generality of the effect and clinical significance. Nominal logistic regression analysis will be used to compare the treatment groups in covariate-adjusted odds of remission. Remission status will be the dependent variable. The independent variables will be the treatment group indicator, along with site, medication resistance, and baseline HRSD₂₄.

Hypothesis 5. In two primary cognitive measures, orientation recovery time and CUAMI-SF scores, FEAST will have a significant advantage relative to UB RUL ECT.

The cognitive measures were described in Section B.12. Orientation time will be averaged within each patient across all treatments. An ANCOVA will be conducted on these values with Site and Treatment Group as between-subject factors, and age and number of treatments in the average as covariates. A similar ANOVA will be conducted on CUAMI-

SF scores, with Site and Treatment Group as between-subject factors, and age, number of treatments, and baseline CUAMI-SF score as the covariates.

Hypothesis 6. FEAST will have a significant advantage in the subjective global evaluation of the effects of ECT on memory.

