Delay in Start of Alternative or Continuation Therapy. Two or three days may elapse between completion of the FEAST/UB RUL ECT course and the completion of post-course research evaluations (e.g., cognitive measures, fMRI, etc.). This interval will occur regardless of clinical outcome of the FEAST/ECT course. At maximum, this delay may extend to 5 days if there are scheduling difficulties. This delay of at most 5 days before starting alternative acute treatment or continuation therapy has the theoretical risk of contributing to or accelerating later relapse. However, it should be noted that in many of our prior research studies we have routinely used a one-week medication-free interval following ECT in order to certify response and/or remission status ([name] et al., 2008, [name] et al., 1987a, [name] et al., 1993, [name] et al., 2000b, [name] et al., 2009). No untoward effect of this practice was noted. However, more critically, during the short delay, patients will not be medication free. They will continue on the medication regimen that was stabilized

before FEAST/ECT and maintained during the FEAST/ECT course. This should mitigate against potential clinical worsening due to the delay in instituting alternative acute treatment (e.g., nonresponders) or continuation therapy (e.g., remitters).

Confidentiality of the Data. It is always important to protect patient confidentiality, and especially so in the treatment of individuals with severe psychiatric disorders. Several steps will be taken to preserve confidentiality. When research papers are written, no participant identifying information will be reported. All records will be kept in locked files and kept confidential to the extent permitted by law. Electronically stored or transmitted information (computerized data) will not contain the name or other identifiers of participants. Participants will be identified in the electronic data by an arbitrary numeric code. The master list linking these numbers to participants' names will be kept in locked files. Any electronic transmission of information about participants will not contain the name or other personal identifiers and will be encrypted.

C.5 Risk Analysis Summary

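### Remission is defined on a 1-week post-ECT HRSD24 that no visit schedules, while the analysis section uses an undated post-treatment score

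*Combined protocol and SAP*

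**What the plan says.** **Outcome definitions (IV.B.9).** "Remission is the categorical outcome that has precedence for efficacy determination". Response comes first: "Based on an assessment 1-2 days following ECT, patients are responders if they have a" reduction of at least 50% in HRSD24 from baseline. Remitters then "must satisfy final response criteria and have a 1-wk postECT HRSD" of 10 or less.

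**Rating times (IV.B.8).** The clinician scales are completed "both at set time points (preECT baseline, 1-2 days after ECT termination"). The only other ratings named in that sentence are taken while treatment is still under way: "the HRSD alone is also completed at spaced intervals (weekly during the ECT course").

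**Schedule (Table 5).** HRSD24 is marked at screening, at the weekly assessments during ECT, at End Of Acute Study (no day given) and in the column headed "2 month, 4 month, 6 month follow-up". There is no 1-week column.

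**Analysis (IV.B.15, Hypothesis 4).** The hypothesis concerns efficacy directly after the course. Final remission status is HRSD24 "of 10 or less at post-treatment", compared by logistic regression as a secondary analysis. Neither a 1-week time nor a response condition appears.

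**What follows the course (IV.C.4, IV.C.2, IV.C.3).** C.4 describes "This delay of at most 5 days before starting alternative acute treatment or continuation therapy" and mentions a one-week interval only as the practice of earlier studies. C.2 and C.3 offer further ECT to patients who have not remitted.

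**The concern.** The remission rule depends on a rating that the schedule does not produce, and the statistical section describes the same outcome in words that fit a different rating. Remission is the categorical outcome ranked first, in an open-label, non-randomized comparison. If two definitions stand, the choice between them could be made after results are known.

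A site that tried to follow B.9 would have to add a day-7 rating on its own initiative. By then the patient may be receiving other ECT or continuation therapy, and the score would no longer describe the FEAST or ultrabrief RUL course alone.

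**Working it through.** The plan states no expected remission rate or sample size for this outcome, so there is no figure to reproduce. The check sets the times and definitions side by side.

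**1. Timing, in days after the last ECT**
- Scheduled post-course HRSD24 (B.8): day 1-2.
- Longest wait before alternative or continuation treatment (C.4): day 5.
- Rating required by B.9: day 7.
- Next HRSD24 in Table 5 after End Of Acute Study: 2 months.

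The required rating falls 7 − 2 = 5 to 7 − 1 = 6 days after the scheduled one, and 7 − 5 = 2 days after the maximum wait.

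**2. Does the missing response condition in B.15 matter?** The percentage reduction at a score of 10, from baseline b, is 100 × (b − 10)/b.
- b = 20: 50.0%
- b = 21 (the entry minimum in Table 2): 52.4%
- b = 25: 60.0%

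At a single time point, a score of 10 or less already implies response for any baseline of 20 or more. The two definitions therefore differ in timing: B.9 needs day 1-2 and day 7; B.15 needs one rating.

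**3. Who is affected,** reading B.15 as the scheduled 1-2 day rating
- Non-responder at day 1-2: not a remitter under either definition. Scorable now.
- Responder with 10 or less at day 1-2: remitter under B.15; under B.9, undetermined until day 7, and could be moved out.
- Responder above 10 at day 1-2: not a remitter under B.15; under B.9, undetermined until day 7, and could be moved in, possibly after further ECT has begun.

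Only day 1-2 responders are affected, and changes can go both ways.

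**4. Weight of one patient.** IV.B.1 aims for 40 completers per group from 60 enrolled.
- 1/40 = 2.5 points; 1/60 = 1.7 points.
- A net change of 4 patients would be 4/40 = 10.0 points or 4/60 = 6.7 points. The 4 is only an illustration.

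**5. Circularity.** C.2 and C.3 tie the offer of further ECT to not having remitted. B.9 cannot settle that for a day 1-2 responder until day 7, which is after the maximum wait in C.4.

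**The case against.** **Importance.** B.9 ranks remission first among categorical outcomes only. B.8 makes total HRSD scores the primary efficacy measure, B.15 calls the remission comparison secondary, and IV.B.5 places the study's main goal in the EEG comparison. This stands, and it limits the point.

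**Whether the definitions differ.** Post-treatment in B.15 has no day and could be shorthand for B.9. End Of Acute Study has no day either, and the SF-36, attitude interview and cognitive tests may be done at any time in the week after ECT. A site could therefore rate HRSD24 near day 7. But B.8 fixes the post-course rating at 1-2 days, nothing schedules a second, and Hypothesis 4 concerns efficacy directly after the course.

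**Contamination.** C.4 gives a maximum delay, not a start day. New treatment before day 7 is possible; nothing shows it will be usual. This stands.

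**Size.** A reader might infer that if, say, 5 to 15% of patients crossed a score of 10 between the two ratings, the remission rate would move by 5 to 15 points. The documents give no crossing rate. The inference also needs every crossing to run in one direction and to change status, whereas crossings can offset and day 1-2 non-responders cannot become remitters under B.9. Only a shift that differs between groups would alter the comparison.

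**Comparability.** A reader might also infer that a 1-week definition breaks comparability with the FEAST pilot (5 of 17 remitted). The pilot account in III.D.6 places remission at the end of the course but gives no rating day, so this cannot be shown. C.4 says many earlier ECT studies used a one-week interval to certify response or remission, so a 1-2 day definition may lose comparability with those.

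**Choice of remedy.** Scheduling a 1-week rating would also remove the mismatch. That is fair, but the rating would still be open to the effect of intervening treatment.

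**Conclusion.** The contradiction is real and should be corrected. From the scheduled data, B.9 remission cannot be scored for patients who have responded at day 1-2, and an improvised day-7 rating could reflect treatment given after the study course. This is a conflict between sections, not merely a missing detail.

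Its reach is limited. The primary HRSD24 model is untouched, and day 1-2 non-responders can be classified as the plan stands. Each reclassified patient is worth 2.5 points in a group of 40, or 1.7 in a group of 60; the number reclassified and the direction of any net change are unknown. It would also go too far to say that unrated patients will be counted as non-remitters or as missing, because the plan does not say how they would be handled.

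The conclusion rests on reading the B.9 wording as a rating about 7 days after the last treatment, and on B.8 governing the day of the End Of Acute Study HRSD24.

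**What to change.** For the analysis, state one remission definition in both B.9 and B.15: HRSD24 of 10 or less at the already scheduled 1-2 day post-course rating, taken before any new treatment. Give End Of Acute Study the matching day in Table 5. If a 1-week rating is wanted, add it to Table 5 as a descriptive measure and record the date on which any new treatment started.

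The cost is wording, with no extra required visit. The definition becomes slightly less stringent and may be less comparable with earlier ECT studies that used a one-week interval.

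Separately, the sponsor should reconcile the statements in C.2 and C.3 that offer further ECT according to remission status with B.9. No clinical rule is proposed here; the analysis definition need not decide that question.

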information that was just presented to them (immediate memory). In depressed patients, these deficits are most marked for unstructured material that requires effortful processing in order to impose organization (Weingartner et al., 1981, Weingartner et al., 1983, Weingartner and Silberman, 1984, Roy-Byrne et al., 1986, Burt et al., 1995, Burt et al., 2000). However, such patients are less likely to have deficits in retaining the new information that they do learn (delayed memory) (Cronholm and Ottosson, 1961, Sternberg and Jarvik, 1976, Steif et al., 1986). During the ECT course, deficits in attention and concentration may be accentuated ([name] et al., 1992b, [name], 1992, Calev et al., 1995). In contrast, with symptomatic response following ECT, these deficits usually resolve. Consequently, measures of immediate memory are either unchanged or improved within a few days of ECT termination (Cronholm and Ottosson, 1961, Steif et al., 1986, Weiner et al., 1986, Rossi et al., 1990, [name] et al., 1993, [name] et al., 2000b, [name] et al., 2007).

Since attention and concentration are essential to many aspects of cognitive function, it is not surprising that shortly following completion of the ECT course improvement may be observed in a wide variety of neuropsychological domains, including global cognitive status ([name] et al., 1993, Sabin et al., 1995b) and measures of general intelligence (IQ) (Huston and Strother, 1948, Stieper et al., 1951, Squire and Chace, 1975, Malloy et al., 1982, [name] et al., 1992a) [see (Semkovska and McLoughlin, 2010) for a recent meta-analysis]. There is no evidence that ECT results in lasting impairments of executive function (e.g., the capacity to shift mental sets), abstract reasoning, creativity, semantic memory, implicit memory, or skill acquisition or retention (Weeks et al., 1980, Frith et al., 1983, Squire et al., 1984, Taylor and Abrams, 1985, Abrams and Taylor, 1985, Jones et al., 1988). Indeed, the fundamental distinction between declarative and nondeclarative memory systems, as formulated by Squire, was based partly on evidence that ECT patients showed deficits in the retention of information consciously recalled or propositional in nature, while retention of procedural learning (mirror reading), classical conditioning, word priming, etc. was unimpaired even shortly following treatments (Squire, 1986a).

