The protocol presented in this new IDE will be performed at two clinical sites (MUSC and GRU). At each site 20 patients will be recruited to receive treatment with FEAST, or a total of 40 FEAST patients across the sites. A contemporaneous group of 20 patients will be identified at each site who are receiving standard clinical treatment with UB RUL ECT. These patients will be matched to the FEAST sample (within site)

in the distribution of gender and diagnosis (unipolar vs. bipolar), and the mean, variance and shape of the distributions of age and baseline modified mini-Mental State score (mMMS) (Stern et al., 1987). This RUL cohort is also included under this IDE. [We considered but ultimately abandoned having a formal, blind randomization of patients to FEAST or RUL. While we ultimately hope to perform such a study, the data with FEAST are quite limited at present. There thus may not be true clinical equipoise. Similarly, although the FEAST side effects appear benign, there have still been less than 50 patients total ever treated with FEAST. We thus have settled on a non-randomized but loosely matched comparison group. This group is important for the analysis of the EEG and MRI data, and can also be used for rough comparison of efficacy and cognitive side effects. It is our hope that following this trial, there might be sufficient evidence of efficacy to enable a formal randomized definitive trial.

We will be applying to the NIH for funding to support the conduct of this protocol. This IDE will serve to gather important pilot data and will serve as the IDE for the NIH study, if it is funded.

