Across the sites 60 patients will be enrolled to achieve 40 FEAST patients who will fully complete this study at the MUSC Institute of Psychiatry, Brain Stimulation Service (BSS) in Charleston, SC, and at GRU in Augusta, GA and Aiken, SC. At both MUSC and GRU, roughly matched 30 patients (each) will also be recruited from those scheduled to receive UB RUL ECT to obtain a cohort of 40 RUL comparison patients. The FEAST and UB RUL ECT groups must meet identical inclusion/exclusion criteria and will undergo identical evaluation procedures. The only difference between the groups will be that one receives FEAST and other UB RUL ECT. The treatment received by the UB RUL ECT group will not be affected by participating in this protocol. This is an open label, non-randomized, non-masked study. Separate consent forms will be used in each group. We are thus asking FDA permission to study 60 patients with FEAST. An additional 60 patients will be studied who receive conventional ECT. Even though they are getting conventional ECT, they are covered by this FDA IDE as their data will be used for comparison purposes with FEAST.

Patients will be selected from those referred for ECT for the treatment of major depressive episode. To verify diagnosis, the SCID-P will be administered to derive DSM-V diagnosis (unipolar or bipolar major depressive episode) and relevant subtypes and specifiers (American Psychiatric Association, 2013).

Inclusion and exclusion criteria are presented in Table 2. Briefly, patients will be between the ages of 18 and 90 years and will provide informed consent. Exclusions include: history of schizophrenia, schizoaffective disorder or any non-mood disorder psychosis, rapid cycling bipolar disorder, central nervous system illness other than conditions associated with psychotropic exposure, alcohol or substance abuse or dependence in the past 3 months, pregnancy, epilepsy, inability to have stable medications, and ECT within the past six months.

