The measures of Clinical Status and Characteristics in Table 3 are essentially unchanged since the original IDE. The cognitive battery is considerably reduced. This was done since the primary goal of this study is the comparison of the groups in EEG manifestations of seizure, with comparisons of efficacy and side effects secondary. Second, none of the dropped measures showed significant change with FEAST administration in our prior analyses, and the literature on traditional ECT has only shown persistent deficits for retrograde memory for autobiographical events ([name], 2014b). The measures that were retained serve a particular purpose: (1) the mMMS at baseline is used for sample characterization and matching of the two groups. A significant difference between the groups would denote an effect pertaining to global cognitive status. This is not expected. (2) Orientation recovery will be assessed at each treatment (but obviously not at preFEAST baseline). This measure has been extremely sensitive to differences in ECT treatment modalities (sine wave vs. brief pulse; ultrabrief vs. brief pulse, BL ECT vs. RUL ECT, etc.) and has been found to predict long-term deficits in autobiographical memory (Sabin et al., 1995b). We expect the FEAST group to manifest faster recovery of orientation than the UB RUL ECT group, even though the latter has manifested remarkably rapid recovery compared to other ECT modalities ([name] et al., 2008). (3) The most critical measure is the CUAMI-SF. This measure has repeatedly shown differences between modalities and has the strongest evidence for persistent deficit following ECT. While effects of UB RUL ECT on this measure have been slight (compared to retested normal controls), nonetheless we predict an advantage for FEAST in this measure of autobiographical amnesia. (4) The Attitudes Interview collects patient self-report on the effects of the treatment course on mood

and memory. A global assessment is given by the patient, akin to a clinical global impression (CGI) for each domain. Recent research has shown that these are the only self-report measures in the history of ECT research to show significant covariation with objective cognitive deficits and with type of ECT modality (Berman et al., 2008, Brakemeier et al., 2011b). We predict that the FEAST and UB RUL ECT groups will be equivalent in self-report of effects on mood, but the FEAST group will report less deleterious impact on memory.

B. 5a MRI scan

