Oreintation recovery time will be assessed at every treatment session. The most profound cognitive effects of ECT are expressed in the postictal period (Daniel and Crovitz, 1983a, Daniel and Crovitz, 1983b, [name], 1986a). The repeated assessment (every treatment) strongly enhances reliability of measurement, and allows for examination of progressive change over the treatment course (Calev et al., 1991a, Calev et al., 1991b, [name] et al., 1986). The measurement of orientation recovery has been particularly sensitive to variation in ECT electrode placement, waveform, and dosage. Further, it has been repeatedly found to be a potent predictor of the degree of retrograde amnesia following the ECT course, even in the long-term (Sobin et al., 1995b). Following seizure termination, orientation (5 items) is assessed continuously until the criterion for full recovery is met or 90 min elapse. The critierion for recovery is correct response to 4 of the 5 items. The 5 questions pertain to name, birth date, age, place, and day of the week.

The mMMS, Buschke Selective Reminding Test (BSRT) and CUAMI-SF will be administered at baseline and at follow-up (during the week following FEAST or UB RUL ECT). The modified form of the MMS provides a total socre of 57 (as opposed to 30 with the original version) and broader coverage of gross cognitive abilities (Mayeux et al., 1981, Stern et al., 1987). The primary use of the mMMS is sample characterization, especially since there is evidence that low baseline scores predict more severe short- and long-term retrograde amnesia (i.e., cognitively-compromised paitents are more vulnerable to the key adverse effect on memory) (Sobin et al., 1995a). No change is expected in mMMS scores in either group. However, as a safety measure, the two groups will be compared in change in mMMS scores to verify this assumption and assure that there was no change in global congitive status.

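### The mMMS safety check compares change between two treated groups, so it cannot verify the stated assumption of no change within either group

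*Combined protocol and SAP*

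**What the plan says.** Section IV.B.12 describes the mMMS mainly as a tool for characterizing the sample, then gives it a safety role. The assumption concerns each group separately: "No change is expected in mMMS scores in either group". The check that follows concerns the difference between groups: "the two groups will be compared in change in mMMS scores to verify this assumption and assure that there was no change" in global cognitive status.

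Section IV.B.5 has a similar sentence, "A significant difference between the groups would denote an effect pertaining to global cognitive status", inside an item about the baseline mMMS and matching.

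The test "will be administered at baseline and at follow-up (during the week following FEAST or UB RUL ECT"), so a change score exists for every assessed patient in both groups.

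Section IV.B.15 contains no mMMS analysis. Hypothesis 5 names orientation recovery time and the CUAMI-SF as its two primary cognitive measures. Nowhere do the documents give, for the mMMS, a within-group test, a confidence interval for change or a tolerable decline.

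**The concern.** The assumption and its verification have different targets. The assumption is that mean change is zero in FEAST and zero in UB RUL ECT. The comparison asks only whether the two mean changes are equal, which is true of any shift the groups share, in either direction.

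The comparator is itself an ECT modality, so whatever the two treatments have in common drops out of the contrast. Matching on baseline mMMS does not help, because it balances the starting level and not the change.

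At stake is one sentence in the trial report. Under the wording of Section IV.B.12, a null comparison would be cited as assurance that global cognition was unchanged after FEAST, although that comparison carries no information on the point. In Table 3 the mMMS is the only instrument listed under global cognitive function. Orientation recovery, the CUAMI-SF and the BSRT measure other things.

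**Working it through.** **Inputs from the documents.** The opening of Section IV plans "a total of 40 FEAST patients across the sites", and Section IV.B.1 recruits "to obtain a cohort of 40 RUL comparison patients", so n = 40 per group. Section IV.B.1 enrols 60 per group, taken here as an upper bound. The plan states no power, alpha, SD or margin for the mMMS check, so there is no planned figure to reproduce.

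**Assumptions.** Two-sided alpha of 0.05. Declines are in units of the SD of mMMS change, because the documents do not give that SD.

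**Step 1: what the planned test sees.** Let the mean changes be D_F (FEAST) and D_R (UB RUL ECT). The null hypothesis is D_F − D_R = 0. If both groups fall by δ, then D_F − D_R = (−δ) − (−δ) = 0 for every δ. The null is true and the test rejects at its nominal rate. A simulation of 20,000 trials at n = 40 per group gave:

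| Shared decline | Between-group test rejects | Within-group test (one arm) rejects |
|---|---|---|
| 0 SD | 5.1% | 5.2% |
| 0.5 SD | 5.0% | 87% |
| 1.0 SD | 5.0% | about 100% |

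**Step 2: what a within-group test sees.** For a paired t-test of a decline of d SD, the noncentrality is d√n with n − 1 degrees of freedom. At n = 40, √40 = 6.32 and the critical value t(0.975, 39) is 2.02.

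| Decline d | d√40 | Power, n = 40 | Power, n = 60 |
|---|---|---|---|
| 0.2 SD | 1.26 | 24% | 33% |
| 0.3 SD | 1.90 | 46% | 63% |
| 0.5 SD | 3.16 | 87% | 97% |
| 0.8 SD | 5.06 | 99.9% | about 100% |

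**Step 3: precision.** The within-group 95% CI half-width is 2.02/√40 = 0.32 SD at n = 40, and 0.26 SD at n = 60. The between-group half-width is 1.96 × √(2/40) = 0.44 SD.

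**Step 4: example.** Suppose the observed fall is 0.5 SD in both groups. The between-group estimate is 0, with an interval of −0.44 to 0.44 SD. The FEAST interval is −0.5 ± 0.32, or −0.82 to −0.18 SD, which excludes zero.

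**Step 5: unequal declines.** At n = 40 per group, between-group power is 14% / 27% / 61% for differences of 0.2 / 0.3 / 0.5 SD. The difference detectable with 80% power is (1.96 + 0.84) × √(2/40) = 0.63 SD. A non-significant result is therefore weak evidence even of similarity between modalities.

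**The case against.** The sponsor has several fair replies.

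- **Importance.** The mMMS is chiefly for sample characterization and belongs to none of Hypotheses 1 to 6. The plan places the main cognitive risk in memory, which the CUAMI-SF and BSRT cover, with orientation assessed at every session. Adverse event reporting also bears on cognition. This stands, and it limits the point to a secondary safety analysis.
- **Reporting.** Comparing groups in change requires computing each group's change, and nothing forbids showing it. The earlier FEAST series in Section III.D.6 reported MMSE before and after treatment (28.4 and 29.1, p = 0.33). This is a fair precedent for the remedy, but the current text does not commit to it and attaches the assurance to the wrong contrast.
- **Role of a comparator.** Uncontrolled pre-post change mixes treatment effect with mood recovery and retest effects, so improvement from recovery could mask harm. This stands. The between-group comparison should be kept and the two results read together.
- **Limits of the remedy.** At n = 40 a within-group test has low power for declines of 0.2 to 0.3 SD. This also stands, and is a reason to rely on the interval and a stated limit instead of a p-value.

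A reader might go further and infer that a shared fall is the most plausible form of harm. The documents do not support that: the pilot MMSE means and Section III.C.5 point to stability or improvement.

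A reader might also infer that Section III.C.5 contradicts the assumption of no change. It does not. It says that "shortly following completion of the ECT course improvement may be observed in a wide variety of neuropsychological domains, including global cognitive status", which is a possibility. Its remark that improvement is typical refers to patients with global impairment before ECT. Nor is the sentence in Section IV.B.5 a clear post-course decision rule, since it sits in an item on baseline use.

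**Conclusion.** The check is wrong as written. A comparison of change between FEAST and UB RUL ECT cannot verify that neither group changed, and it gives no assurance about global cognitive status after FEAST. The cancellation is algebraic and needs no assumption about the SD. The 5% rejection rate under a shared decline assumes a two-sided alpha of 0.05. The power and precision figures also assume 40 analysed patients per group and are in SD-of-change units, because no SD is given.

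The consequence is confined to a secondary safety statement; no primary hypothesis is affected. The finding is that the planned check could not reveal a shared change if one occurred. It is not evidence that a shared decline is expected, or that the plan would set aside a decline visible in both groups.

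**What to change.** In Section IV.B.12:

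1. Report mean mMMS change from baseline to the post-course assessment, with a 95% CI, separately for FEAST and UB RUL ECT.
2. Base any statement of no change or no decline in global cognitive status on those within-group intervals, judged against a tolerable decline that the sponsor fixes before analysis.
3. Keep the between-group comparison, described as the test of a difference between modalities, and delete the statement that it assures no change.
4. State that within-group change is uncontrolled and reflects mood recovery and retest effects as well as treatment, so the two summaries are to be read together.

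Add a matching line to Section IV.B.15, which has no mMMS analysis. The cost is a few sentences, one table and agreement on the tolerable decline. No new data are needed, because the mMMS is already collected before and after the course in both groups.
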